2. STUDY OBJECTIVES

Specific objectives and corresponding endpoints for the master study and sub-studies are outlined in Table 5 and Table 6 below. Additional objectives and endpoints may be specified according to the relevant sub-protocol.

The Phase 1b objectives will only apply to sub-studies of DAY101 in combination with other therapies (Table 5).

The Phase 2 objectives will apply to the investigation of DAY101 as monotherapy and in combination with other therapies. Additional objectives will be specified according to the relevant sub-protocol (Table 6).

Table 5: Phase 1b Study Objectives and Endpoints

PRIMARY OBJECTIVE AND ENDPOINTS IN PHASE 1B	
OBJECTIVE	ENDPOINTS
To determine the safety of DAY101 in combination with other therapies.	
Incidence and severity of adverse events, with severity determined according to National Cancer Institute Common Terminology Criteria for Advanced Tumours (NCI CTCAE) v5Change from baseline in targeted vital signsChange from baseline in targeted clinical laboratory test results
To determine the maximum tolerable dose (MTD) and recommended Phase 2 dose (RP2D) of DAY101 in combination with other therapies.	
Incidence and severity of adverse events, with severity determined according to NCI CTCAE v5Change from baseline in targeted vital signsChange from baseline in targeted clinical laboratory test resultsIncidence of dose-limiting toxicities (DLTs)
SECONDARY OBJECTIVES AND ENDPOINTS IN PHASE 1B	
OBJECTIVE	ENDPOINTS
To assess the efficacy of DAY101 in combination with other therapies by Response Evaluation Criteria in Solid Tumors (RECIST) version 1.1 or appropriate tumor response criteria.	
ORR as assessed by the proportion of patients with the best overall confirmed response of complete response (CR) or partial response (PR) according to the appropriate tumor response criteria as assessed by InvestigatorDuration of response (DOR) in patients with best overall response of CR or PR as determined by the treating Investigator [from time of first tumor response to progression or date of data analysis, whichever occurs earlier]Duration of progression-free survival (PFS) following initiation of study treatment to disease progression,

	
death, or date of analysis, whichever occurs earlier according to the appropriate tumor response criteriaDuration of overall survival (OS) following initiation of study treatment to time of deathTime to response (TTR) in patients with best overall response of CR or PR as determined by treating Investigator [from initiation of study treatment to date of first response]Comparing the DOR in patients with CR or PR as determined by treating Investigator with the DOR observed with the immediate prior line of anticancer treatment
To characterize the pharmacokinetic (PK) profile of DAY101 in combination with other therapies.	
Plasma concentration of DAY101 at specified time points in order to define PK parameters
To characterize pharmacodynamic (PD) effects of DAY101 in combination with other therapies.	
PD to be assessed by relevant assay or platform including but not limited to RNA sequencing and immunohistochemistry (Please see Appendix E).
EXPLORATORY OBJECTIVES AND ENDPOINTS IN PHASE 1B	
OBJECTIVES	ENDPOINTS
To evaluate the genomic profile of archival tumor biopsies or fresh tumor biopsies (if available) from patients who will be treated with DAY101 in combination with other therapies.	
Assess genomic alterations from archival tumor biopsy or fresh tumor specimens using a relevant platform(s) such as, but not limited to, next-generation sequencing and circulating tumor DNA (ctDNA)
To characterize pathway modulation, and/or genomic alterations in tumor biopsies.	
To characterize genomic alterations in ctDNA.	

Table 6: Phase 2 Study Objectives and Endpoints

PRIMARY OBJECTIVE AND ENDPOINTS IN PHASE 2	
OBJECTIVE	ENDPOINTS
To evaluate the efficacy of DAY101 by RECIST version 1.1 or appropriate tumor response criteria as a monotherapy, or in combination with other therapies.	
 Overall response rate (ORR) as assessed by the proportion of patients with the best overall confirmed response of complete response (CR) or partial response (PR) according to the appropriate response assessment criteria for the disease setting as assessed by the Investigator
SECONDARY OBJECTIVES AND ENDPOINTS IN PHASE 2	
OBJECTIVE	ENDPOINTS
To assess the safety and tolerability of DAY101 as monotherapy, or in combination with other therapies.	
 Incidence and severity of adverse events, with severity determined according to NCI CTCAE v5 Change from baseline in targeted vital signs Change from baseline in targeted clinical laboratory test result
To assess additional efficacy parameters of DAY101 as monotherapy or in combination with other therapies.	
 DOE in patients with best overall response of CR or PR as determined by the treating Investigator [from time of first tumor response to progression or death, whichever occurs earlier] Duration of progression-free survival (PFS) following initiation of study treatment to disease progression or death, whichever occurs earlier according to the appropriate tumor response criteria Duration of OS following initiation of study treatment to time of death
To characterize the tumor responses observed with DAY101 as monotherapy or in combination with other targeted therapies.	
 Time to response (TTR) in patients with best overall response of CR or PR as determined by treating Investigator [from initiation of study treatment to date of first response]
To characterize the pharmacokinetic (PK) profile of DAY101 in combination with other therapies.	
 Plasma concentration of DAY101 at specified time points in order to define PK parameters
To characterize pharmacodynamic (PD) effects of DAY101 in combination with other therapies.	
 PD to be assessed by relevant assay or platform including but not limited to RNA sequencing and immunohistochemistry (Please see Appendix E).
To determine the relationship between PK and PD of DAY101 in combination with other therapies.	
 Determine the relationship between PK and PD biomarkers

EXPLORATORY OBJECTIVES AND ENDPOINTS IN PHASE 2	
OBJECTIVES	ENDPOINTS
To evaluate the genomic profile of archival tumor or fresh tumor biopsies from patients who will be treated with DAY101 as monotherapy or in combination with other therapies.	
• Assess genomic alterations from archival or fresh tumor biopsy specimens using a relevant platform such as but not limited to ctDNA and next-generation sequencing
To characterize pathway modulation and/or genomic alterations from tumor biopsies.	
To characterize genomic alterations from ctDNA.	

3. INVESTIGATIONAL PLAN

3.1. Study Design

This is a Phase 1b/2, multi-center, open-label, umbrella study of patients \geq 12 years of age with recurrent or progressive solid tumors with alterations in the key proteins of the RAS/RAF/MEK/ERK pathway, which will be referred to as the MAPK pathway. Patients with these alterations will be identified through molecular assays as routinely performed at Clinical Laboratory Improvement Amendments of 1988 (CLIA) or other similarly certified laboratories.

Based on the identified alterations in the key proteins of the MAPK pathway, patients may be offered the opportunity to participate in one or more sub-protocols within this umbrella study of DAY101 as monotherapy or in combination with other therapies. Enrollment will be based on the specific eligibility criteria described in each sub-protocol.

Study DAY101-102 (master study) and sub-protocols consist of a screening period, a treatment period, a safety follow-up period, and a long-term follow-up (LTFU) period where survival status, and subsequent anticancer therapies will be collected.

DAY101 will be administered as specified in the sub-protocol. Additional dose schedules may be explored. Dose level(s), dose schedule(s), and cycle lengths for DAY101 as monotherapy or in combination with other therapies will be specified in each sub-protocol.

Cycles will repeat, as specified in each sub-protocol, until disease progression, unacceptable toxicity, withdrawal of consent, or death.

Patients will undergo radiographic evaluation of their disease at baseline, at the end of [REDACTED] for 1 year and then [REDACTED] thereafter, or as specified in a given sub-protocol. Generally, response assessment will be performed according to Response Evaluation Criteria in Solid Tumors (RECIST) version 1.1 for solid tumors. Alternative criteria may be used in specific disease settings, such as glioma, where response assessment will be assessed by RANO criteria. Appropriate response criteria for tumors are described in Appendix B and Appendix C.

[figure not shown]
Patients who have radiographic evidence of disease progression may be allowed to continue DAY101 (and combination partner if applicable) if, in the opinion of the Investigator, the patient is deriving clinical benefit from continuing study treatment, and continuation of treatment is approved by the Sponsor.

DAY101 for oral dosing is provided a white to off-white [REDACTED] powder as an immediate-release 100 mg tablet. The 100 mg tablets are red to yellowish-red oval tablets. All products are labeled DAY101.

Other therapies may be included in future sub-protocols and will be further specified within each sub-protocol.

Scheduled activities will be performed in as outlined in the Schedule of Activities within each sub-protocol. The study design schema is shown in Figure 3. Refer to the relevant sub-protocol for each sub-protocol design schema.

Figure 3: Study Design Schema

3.1.1. End of Study and Length of Study

For details related to end of study and length of study, please see relevant sub-protocols.

3.1.2. Number of Patients

Maximum number of patients enrolled will be dependent on the sub-studies included. Please refer to specific sub-protocol for more detail.

3.2. Investigational Sites

Refer to the sub-protocols for the number of institutions participating in this study.

4. SELECTION OF STUDY POPULATION

Potential patients and/or their parents must sign an informed consent form (ICF) and pediatric assent form, where applicable, before any study-specific screening tests may be conducted. Inclusion and exclusion criteria can be found within each sub-protocol.

5. TREATMENT

5.1. Investigational Product

DAY101 for oral dosing is a white to off-white [REDACTED] powder formulated as a 100 mg immediate-release tablet. The 100 mg tablets are red to yellowish-red oval tablets. All products are labeled DAY101.

The site pharmacist will dispense the tablets to the patient, or to the patient's parent or legal guardian, in an amount necessary to allow for outpatient administration. Further information is provided in the Pharmacy Manual.

DAY101 tablets are to be stored at controlled room temperature (between 15°C and 30°C) and protected from light. Additional details regarding the investigational product are provided in the DAY101 IB.

Additional therapies may be included. For further details, please see relevant sub-protocols.

5.2. DAY101 Administration

5.2.1. General Dosing Instructions

Dosing for an individual should be at a consistent day and time (\pm 12 hours) each week. There is no restriction with regard to intake of food (patients can be fed or fasted). Tablets must not be cut or crushed.

If the patient vomits the tablets and they are still recognizable, then the patient can be re-dosed. If the patient vomits within 30 minutes of ingesting tablets and the tablets are not recognizable, the patient or parent or legal guardian should be instructed to call the Investigator or study nurse to discuss whether the patient should take any additional tablets. If it has been longer than 30 minutes or the Investigator or study nurse is not reachable, the patient should not be re-dosed.

The patient, or the patient's parent or legal guardian, will complete a study drug administration diary to record dosing compliance. The study drug administration diary will be reviewed at each clinic visit by the Investigator or study nurse. The study drug administration diary will also be assessed at each clinic visit.

For additional dosing administration instruction for each sub-protocol, please refer to individual sub-protocol for details.

5.2.2. Dose-Limiting Toxicity

Assessment of DLT will be further specified in relevant sub-protocols.

5.2.3. Dose Modifications

Please refer to the sub-protocols for study drug modifications and reduction details.

5.2.4. Management of Treatment-Related Events

Please refer to the sub-protocols for study drug modifications and treatment-related events management guidelines for DAY101 and/or combination partners.

5.3. Removal of Patients from Therapy or Assessment

Patients may withdraw from the study at any time. Patients who withdraw from therapy and do not withdraw consent will be referred to as “discontinue study treatment” and will be followed for LTFU. Over the course of the study, a patient may discontinue from study treatment for any of the reasons listed below:

- Disease progression as assessed by the Investigator, except if, in the opinion of the Investigator and with permission of the Sponsor, the patient is deriving clinical benefit from continued study treatment
- Unacceptable toxicity
- Intercurrent illness compromising the ability to fulfill protocol requirements
- Dosing interruption > 28 days, unless resumption of treatment approved by the Sponsor
- Requirement for alternative treatment in the opinion of the Investigator
- Significant noncompliance to protocol
- Pregnancy
- Withdrawal of consent or assent by the patient or the patient’s parent or legal guardian
- Loss to follow-up
- Death

When a patient discontinues from treatment, the patient will undergo the end of treatment (EOT) visit, as outlined in Section 6.24 .

5.4. Prior and Concomitant Medications

5.4.1. General

All medications that were used from 28 days prior to enrollment through 30 days following the last dose of study drug will be recorded in the eCRF. All prior anticancer treatments, regardless of when they were administered, will also be collected. These are to include prescription medications and transfusions. Excluded prior medications are those excluded via the eligibility criteria. Please refer to the sub-protocols for eligibility criteria and specific concomitant medication information.

5.4.2. Allowed Concomitant Medications

Please refer to the sub-protocols for specific allowed concomitant medications.

5.4.3. Prohibited Concomitant Medications

Please refer to the sub-protocols for specific prohibited concomitant medications.

5.4.4. Palliative Radiotherapy

In general, measurable lesions being used to measure response should not be irradiated without discussion with the Sponsor and may be reason for the patient to be removed from study for progressive disease. Irradiated non-measurable lesions will be considered not evaluable for response, but still can be used to assess progressive disease. The intensities, number, and dates of doses received for allowed palliative radiotherapy should be recorded on the appropriate eCRF.

Please see each sub-protocol for instruction on holding DAY101 and other investigational drugs.

5.4.5. Concurrent Surgery

Patients may undergo surgical intervention and remain on study when, in the opinion of the treating Investigator, surgery is indicated for anything other than tumor resection for clinical or radiographic disease progression. Therapy should be held for 6 days before surgical intervention. Patients undergoing surgical intervention are permitted to restart study treatment 6 days following surgical intervention after discussion with and approval by the Sponsor. The surgical intervention should be recorded on the appropriate electronic case report form (eCRF). For patients requiring surgical intervention due to clinical or radiographic evidence of tumor progression, patients should be withdrawn from study.

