6.21. Survival Status

Patients will be followed for survival status, date of progression, and subsequent anticancer therapies by telephone or any other method.

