6.26. Long-Term Follow-up

After study treatment discontinuation, LTFU assessments will occur approximately every 3 months (\pm 1 month) until the patient withdraws consent for further participation, is lost to follow-up, has died, or the study is closed. For any patient who discontinues study treatment prior to disease progression, tumor assessment will progress accordingly as if on study treatment and will be requested to return to site for continued monitoring and assessment. After progression and in LTFU, the site will contact the patient or the patient's parent/legal guardian for follow-up assessments that may include subsequent anticancer therapies and survival status. LTFU may be conducted by telephone except for those patients who have not yet progressed after treatment discontinuation. For any patient who is lost to follow-up, the study site will attempt to ascertain survival information via public database search. If survival status still cannot be ascertained, patients will be considered lost to follow-up. The first LTFU assessment will occur 3 months (\pm 1 month) after the EOT visit.

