##### **3.3.2.3. Progression Free Survival**

PFS is defined as the interval from the date of the first dose to the first occurrence of radiographic disease progression based on RECIST 1.1 or RANO criteria or death due to any cause, whichever occurs earlier. If a patient does not experience progression or death by the data cutoff date, then the patient will be censored at the date of the last evaluable tumor assessment. Patients who complete treatment or withdraw from treatment but do not withdraw consent from the study will continue to be followed for progression during the long-term follow-up (LTFU). Patients with no relevant tumor response assessment will be censored at the start of treatment. See Appendix 6.3 for complete censoring rules for PFS.

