##### **3.3.2.4. Overall Survival**

OS is defined as the interval from the date of the first dose until the recorded date of death due to any cause. Patients who are still alive and patients lost to follow-up will be censored on the date when they were last known to be alive.

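### Protocol 5.4.5 withdraws patients who need surgery for progression from the study, while 5.3, 6.21, 6.26 and the SAP keep such patients in follow-up; taken literally, 5.4.5 makes OS censoring informative

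*Protocol*

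**What the plan says.** Protocol 5.4.5 (Concurrent Surgery) lets patients stay on study when surgery is for a reason other than resection for progression, with therapy held and later restarted. For the other group it says: "For patients requiring surgical intervention due to clinical or radiographic evidence of tumor progression, patients should be withdrawn from study". It does not mention survival, long-term follow-up (LTFU) or consent. Section 5.4.4 (Palliative Radiotherapy) has similar wording: irradiating a measurable lesion may lead to removal from the study for progressive disease.

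The sections that govern follow-up read differently:

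- Protocol 5.3 lists disease progression among the grounds on which "a patient may discontinue from study treatment for any of the reasons listed below". Patients who leave therapy without withdrawing consent stay in the trial "and will be followed for LTFU".
- Protocol 6.21, with no exception for surgery: "Patients will be followed for survival status, date of progression, and subsequent anticancer therapies by telephone or any other method".
- Protocol 6.26 runs LTFU "until the patient withdraws consent for further participation, is lost to follow-up, has died, or the study is closed". After progression it provides for "follow-up assessments that may include subsequent anticancer therapies and survival status".
- SAP 3.3.2.3: "Patients who complete treatment or withdraw from treatment but do not withdraw consent from the study will continue to be followed for progression".

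For OS, SAP 3.3.2.4 states that patients still alive and "patients lost to follow-up will be censored on the date when they were last known to be alive". It has no rule for withdrawal because of surgery.

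**The concern.** Kaplan-Meier estimation assumes that patients who are censored have the same later risk as those still followed. A patient who leaves the study because the tumour has progressed to the point of surgery does not fit that assumption. If sites apply 5.4.5 as written, the last date known alive falls near the operation and later deaths in this group are not counted. The patients still at risk are then weighted towards those who have not progressed, so the OS curve sits too high.

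PFS and DOR have a narrower exposure. The SAP event is radiographic progression or death. Section 5.4.5 also covers surgery for clinical progression, and such a patient may leave before any scan qualifies.

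**Working it through.** **1. Is the wording only shorthand for stopping drug?** Section 5.4.5 speaks separately of holding therapy, restarting study treatment and staying on study. Section 5.3 separates withdrawing from the study from discontinuing treatment, and SAP 3.4.1 tabulates the two separately. A site could reasonably record a study exit.

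**2. Does any follow-up section support an exit?** No. Neither surgery nor progression is among the four events that end LTFU in 6.26. Sections 5.3 and 6.21 and SAP 3.3.2.3 contain no exception for surgery.

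**3. Which endpoints are exposed if 5.4.5 is applied literally?**

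| Endpoint | Rule | Effect |
|---|---|---|
| ORR (primary) | SAP 3.2.1: patients with measurable disease and at least one dose; no post-baseline assessment counts as non-response | Denominator unchanged |
| PFS, DOR with documented radiographic progression | SAP Appendix 6.3: event at the earliest progression date; SAP 3.7.1 applies similar rules to DOR | None; later withdrawal does not remove the event |
| PFS, DOR with clinical progression and no qualifying scan | SAP Appendix 6.3: censored at the last evaluable assessment | Exposed |
| OS | SAP 3.3.2.4: censored when last known alive | Exposed |

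**4. Size for OS (illustration).** The plan has no figure to reproduce; the design inputs in SAP Table 1 are redacted. Inputs:

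- Median time to progression m1 = 5.7 months, the median PFS reported in Protocol 1.2.2.2 for the treatment-naive melanoma cohort of Study C28001; also 3 and 9 months (assumed).
- Median survival after progression m2 = 4, 8 or 12 months (assumed).
- Share f of progressing patients lost at progression = 5% to 30% (assumed).
- Exponential times, no death before progression, and the same risk after progression in lost and retained patients (assumed).

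Let a = ln 2/m1 and d = ln 2/m2. The proportion not yet progressed is P0 = exp(−at). The proportion progressed and alive is P1 = a/(d − a) × [exp(−at) − exp(−dt)]. With a share f lost, Kaplan-Meier sees the hazard

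h(t) = d(1 − f)P1 / [P0 + (1 − f)P1], and S(t) = exp(−∫h).

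Check at f = 0, m1 = 5.7, m2 = 8: a = 0.1216, d = 0.0866, and at t = 16.48 months S = (0.0866 × 0.1348 − 0.1216 × 0.2398)/(0.0866 − 0.1216) = 0.50. The true median is therefore 16.5 months.

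| m1, m2 (months) | f = 0 | 5% | 10% | 20% | 30% |
|---|---|---|---|---|---|
| 5.7, 8 | 16.48 | 16.73 | 17.00 | 17.60 | 18.33 |
| 3, 12 (smallest bias) | 16.74 | 16.87 | 17.00 | 17.32 | 17.68 |
| 9, 4 (largest bias) | 15.22 | 15.61 | 16.02 | 17.00 | 18.20 |

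In the central row, 10% lost gives 17.00/16.48 = 1.032, or 3.2% too high. Over all nine combinations of m1 and m2 the bias is about 1-3% at f = 5%, 2-5% at 10%, 3-12% at 20% and 6-20% at 30%.

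**5. Size for PFS (illustration).** If a share g of progressions is clinical only and censored at that time, the observed hazard is multiplied by 1 − g and the median becomes m1/(1 − g). From 5.7 months this gives 6.0 at g = 5% and 6.3 at g = 10%. Here g is the clinical-only share, not the share having surgery, so it must be smaller than the surgery rate if some operations follow documented radiographic progression.

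**The case against.** The strongest reply is that 5.4.5 never says follow-up stops. Every section whose subject is follow-up says it continues, and 5.4.4 suggests that the authors sometimes wrote study when they meant treatment. This stands against the stronger reading that a reader might infer, namely that the protocol definitely ends survival and progression follow-up for these patients. The documents support a contradiction, with loss of follow-up only if a site gives the specific surgery rule precedence. The reply does not remove the contradiction.

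A second reply is that most of the PFS problem does not come from 5.4.5, and this largely stands. Documented radiographic progression is already an event on its own date. Clinical-only progression has no event under SAP 3.3.2.3 whatever 5.4.5 says, and if surgery counts as new anticancer treatment, Appendix 6.3 censors at the last assessment before it anyway. In patients assessed by RANO, clinical deterioration is itself listed under progressive disease (SAP Appendix 6.2), which fits poorly with a radiographic-only event. A reader might infer a large PFS bias by setting the censored share equal to a high surgery rate, but that treats every operation as clinical-only, and the documents give no basis for it.

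Third, the consequences are limited. OS, PFS and DOR are secondary, descriptive endpoints in a non-randomised sub-study that the sponsor stopped early (SAP 2.2.1). Remaining patients leave after at least 6 months from first dose, which truncates survival follow-up in any case. All of this stands, and it limits the weight of the point. The master protocol also refers to sub-protocol 102b, so the wording still matters beyond 102a. The sub-protocols are not among the documents and may settle the question.

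**Conclusion.** The inconsistency is real. Section 5.4.5 conflicts with Protocol 5.3, 6.21 and 6.26 and with SAP 3.3.2.3 on whether a patient operated on for progression leaves the study. If 5.4.5 is followed literally, OS censoring depends on progression, and median OS would be overstated by about 1-5% at a 5-10% loss. That range rests on the assumed loss, the exponential model, and lost patients having the same risk after progression as other progressed patients. If patients fit for surgery live longer than other progressed patients, the bias would be smaller. It also leaves out the early stop, after which the median may not be reached.

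PFS and DOR are exposed only for progression without a qualifying scan, and there the SAP's event and censoring definitions matter more than 5.4.5. The ORR denominator is unaffected. How many patients, if any, left this way cannot be known from the documents.

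**What to change.** - **Protocol 5.4.5 and 5.4.4:** reconcile with 5.3, 6.21 and 6.26 by stating that, whatever the treatment decision, survival and progression follow-up under 6.26 continues unless consent is withdrawn. This concerns follow-up status only; no treatment rule is proposed.
- **SAP Appendix 6.3:** state whether surgery for progression counts as new anticancer treatment, and how progression without a qualifying scan is handled for PFS and DOR, including in patients assessed by RANO. No new rule is needed for documented radiographic progression.
- **Reporting for 102a:** give the number of patients who left the study under 5.4.5, with the date last known alive and whether radiographic progression had been documented. If the number is zero, the point has no effect on the 102a results.

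The cost is a sentence or two in the protocol, a clarification in the SAP and one line in the disposition table. LTFU is already in place. For 102a an amendment can recover little after the early stop, so the count is the useful part there; the protocol wording matters for any other sub-protocol run under the same master.
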